12.0 CONCOMITANT MEDICATIONS

Medications taken at baseline will be recorded in the source and in CRF.

Concomitant medication limitations are described in section 9.5

13.0 ADVERSE EVENTS

13.1 Adverse Event

According to ICH guidelines (Federal Register. 1997; 62(90):25691-25709) and 21 CFR 312.32, IND Safety Reports, and ICH E2A, Definitions and Standards for Expedited Reporting, an adverse event is defined as follows:

An adverse event is any untoward medical occurrence in a clinical investigation subject administered a medicinal product and which does not necessarily have a causal relationship with this treatment. An AE can therefore be any unfavorable and unintended sign (including an abnormal laboratory finding), symptom, or disease temporally associated with the use of a medicinal product, whether or not considered related to the medicinal product.

Abnormal laboratory values for laboratory parameters specified in the study should not be recorded as an adverse event unless an intervention is required (repeat testing to confirm the abnormality is not considered intervention), the laboratory abnormality results in a serious adverse event or the adverse event results in study termination or interruption/discontinuation of study treatment.

Medical conditions present at screening (i.e., before the study treatment is administered) are not adverse events and should not be recorded on adverse event pages of the CRFs. These medical conditions should be adequately documented on the subject chart. However, medical conditions present at baseline that worsen in intensity or frequency during the treatment or post-treatment periods should be reported and recorded as adverse events.

13.2 Serious Adverse Event

An adverse event should be classified as an SAE if it meets one of the following criteria:

| | |
|-------------------------------------|--|
| Fatal | Adverse event results in death. |
| Life threatening: | The adverse events placed the subject at immediate risk of death. This classification did not apply to an adverse event that hypothetically might cause death if it were more severe. |
| Hospitalization: | It required or prolonged inpatient hospitalization. Hospitalizations for elective medical or surgical procedures or treatments planned before enrollment in the treatment plan or routine check-ups are not SAEs by this criterion. Admission to a palliative unit or hospice care facility is not considered to be a hospitalization. |
| Disabling/incapacitating | Resulted in a substantial and permanent disruption of the subject's ability to carry out normal life functions. |
| Congenital anomaly or birth defect: | An adverse outcome in a child or fetus of a subject exposed to the molecule or treatment plan regimen before conception or during pregnancy. |
| Medically significant: | The adverse event did not meet any of the above criteria but could have jeopardized the subject and might have required medical or surgical intervention to prevent one of the outcomes listed above. |

13.3 Unexpected Adverse Event

An unexpected adverse event is defined as an event that has a nature or severity, or frequency that is not consistent with the known risks of acupuncture or acupressure, or the prior medical condition of the subject or other treatment given to the subject. "Unexpected," as used in this definition, refers to an adverse experience that has not been previously observed and reported in preclinical or clinical studies of acupuncture and acupressure.

13.4 Monitoring and Recording Adverse Events

All AEs will be assessed by the investigator or qualified designee and recorded in the CRFs. The investigator should attempt to establish a diagnosis of the event on the basis of signs, symptoms and/or other clinical information. In such cases, the diagnosis should be documented as the adverse event and/or serious adverse event and not described as the individual signs or symptoms. The following information should be recorded:

- Description of the adverse event using concise medical terminology
- Description as to whether or not the adverse event is serious, noting all criteria that apply
- The start date (date of adverse event onset)
- The stop date (date of adverse event resolution)
- The severity (grade) of the adverse event
- A description of the potential relatedness of the adverse event to a study procedure or other causality
- The action taken due to the adverse event
- The outcome of the adverse event

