6.3.2 Secondary Endpoints

Incidence of grade 2 or higher CIPN as measured by CTCAE version 5.

Severity of CIPN as measured by a Neuropen and tuning fork.

Proportion of patients assigned to the intervention arm who complete 60% of acupuncture treatments.

Incidence of pain, fatigue, nausea, oral dysesthesia, and anxiety as measured by the NCI PRO-CTCAE, BPI, and CTCAE version 5.

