10.0 SUBJECT EVALUATION

10.1 On-Study Clinical Evaluations

Clinical evaluations take place according to the Study Calendar (Appendix B). The window between these visits should be as close to the scheduled time as possible, though delays in chemotherapy treatment as recommended by the treating physician are permitted and do not require cessation of protocol therapy.

- **Vitals**
 - Include blood pressure, pulse, temperature
- **Physical Exam**
- **Performance Status**
 - As per the ECOG performance scale (see Appendix A)
- **Labs (day 1 of each cycle, or up to 3 days prior):**
 - Hematology: CBC with absolute neutrophil count and platelets
- **Acupressure Diary (see Appendix J)**
 - Assessment of self-administered acupressure will be reviewed on day 1 of cycle 2 and each subsequent cycle. Patients who complete <50% of the prescribed acupressure regimen will be re-educated at cycle 2 on appropriate execution of the recommended acupressure regimen.
- **Clinical AE attribution**
 - CTCAE version 5.0

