10.2 Quality of Life Assessments

These will be administered at baseline, 6 weeks, and 12 weeks. If a patient is receiving chemotherapy on the day of the assessments, the assessments must be completed before the chemotherapy treatment is administered.

At each time point the EORTC QLQ CIPN-20 (see Appendix D) will be used to assess neuropathy and targeted questions from the NCI-PRO CTCAE (Appendix E) for the assessment of fatigue, nausea, and anxiety. The Brief Pain Inventory (Appendix F) will be used to assess pain. An oral symptoms questionnaire (Appendix G) will be used to assess oral dysesthesia.

On cycle 4 day 8 (± 2 days), a mid-cycle assessment will be done for the EORTC-QLQ CIPN-20, NCI-PRO CTCAE, and BPI. This may be administered by phone, on paper and returned at next clinic appointment, or electronically.

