13.5 Grading Adverse Event Severity

All AEs will be graded in severity according to the NCI Common Terminology Criteria for Adverse Events (CTCAE) Version 5.0. If a CTCAE criterion does not exist, the investigator should use the grade or adjectives: Grade 1 (mild), Grade 2 (moderate), Grade 3 (severe), Grade 4 (life-threatening), or Grade 5 (fatal) to describe the maximum intensity of the adverse event.

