16.2.2 Secondary Endpoints

- Incidence of grade 2 or higher CIPN as measured by CTCAE version 5
- Severity of CIPN as measured by a Neuropen and tuning fork.
- Proportion of patients assigned to the intervention arm who complete 60% of acupuncture treatments.
- Incidence of pain, fatigue, nausea, and anxiety as measured by patient-reported (NCI PRO-CTCAE, BPI, oral dysesthesia) and provider-assessed (CTCAE version 5) grading scales.

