16.5 Statistical Analysis

Severity of CIPN (EORTC-CIPN-20 score) at 3 months will be summarized for each treatment arm, and treatment comparisons made via linear regression model with adjustment for baseline severity level. Adherence to acupuncture treatment among patients in the intervention arm will be described as a proportion with 95% confidence interval. Reasons for treatment non-adherence and delivered dose intensity of chemotherapy will be noted. Incidences of CIPN (grade 2 or higher), pain, fatigue,

nausea, and anxiety will be compared between treatment arms using Chi-squared or Fisher's exact tests as appropriate. As this is a pilot study, we will not have adequate power to adjust for covariates such as age, gender, and existing comorbidities.

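### The rule in section 13.4 to record the diagnosis and not the symptoms can under-count the provider-assessed CTCAE part of the pain, fatigue, nausea and anxiety endpoint

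*Combined protocol and SAP*

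**What the plan says.** Section 13.4 sets a diagnosis-first rule for adverse events: "The investigator should attempt to establish a diagnosis of the event on the basis of signs, symptoms and/or other clinical information". Where that succeeds, "the diagnosis should be documented as the adverse event and/or serious adverse event and not described as the individual signs or symptoms".

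The same symptoms are endpoints. Section 16.2.2 lists "Incidence of pain, fatigue, nausea, and anxiety as measured by patient-reported (NCI PRO-CTCAE, BPI, oral dysesthesia) and provider-assessed (CTCAE version 5) grading scales". Section 6.3.2 has a similar entry, "Incidence of pain, fatigue, nausea, oral dysesthesia, and anxiety as measured by the NCI PRO-CTCAE, BPI, and CTCAE version 5". Section 16.5 then states the comparison: "nausea, and anxiety will be compared between treatment arms using Chi-squared or Fisher's exact tests as appropriate".

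For the clinician's grades, 13.5 says "All AEs will be graded in severity according to the NCI Common Terminology Criteria for Adverse Events (CTCAE) Version 5.0", and 10.1 lists CTCAE version 5.0 under "Clinical AE attribution". The study calendar (Appendix B) has one row for adverse event assessment, on Day 1 of Cycles 1 to 6 and at the end-of-treatment visit. Patient-reported data are collected separately: 10.2 uses "targeted questions from the NCI-PRO CTCAE (Appendix E) for the assessment of fatigue, nausea, and anxiety", and the BPI for pain.

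**The concern.** A diagnosis-first rule is normal for safety reporting, because it keeps one illness from appearing as several events. Here the same record also appears to supply the provider-assessed half of a secondary endpoint. A clinician who follows 13.4 correctly will leave out an endpoint symptom whenever it has been explained by a diagnosis, and nothing in 13.4 exempts pain, fatigue, nausea or anxiety.

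The case closest to this trial's purpose is pain. Items 5 and 6 of the EORTC QLQ-CIPN20 (Appendix D) treat burning or shooting pain in the hands and feet as a neuropathy symptom. Under 13.4 a clinician would enter such pain as CIPN, and the pain would not be counted as pain. The trial's hypothesis is that the arms differ in CIPN, so this loss would differ by arm through the treatment effect itself. The provider-assessed and patient-reported results could then disagree for no reason but the recording rule.

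**Working it through.** The plan gives no figure for this comparison. The power statement in 16.3 concerns the EORTC-CIPN-20 score only, and 16.5 gives no symptom rates. The check is therefore a reading of the sections against each other, followed by short algebra for the direction of the effect.

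**Step 1. Which record supplies the CTCAE count?**

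| Place | What it provides |
|---|---|
| 10.1 | CTCAE 5.0, named only under adverse event attribution; no list of symptoms to grade |
| 13.5 | Grading of adverse events that have been recorded |
| Appendix B | 6 Day 1 assessments + 1 end-of-treatment assessment = 7 scheduled adverse event assessments; no symptom checklist |
| 13.4 | How events are entered; no exception for endpoint symptoms |

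No section describes grading a named symptom in its own right. As written, the adverse event record is the only source.

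**Step 2. What does 13.4 do to a symptom?** With no diagnosis established, the symptom is entered and graded. With a diagnosis established, the diagnosis is entered and the symptom is not. Only the second kind is lost.

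**Step 3. Effect on incidence.** In one arm, let p be the true proportion of patients with the symptom. Let a be the share of those patients whose every occurrence in the counting period was entered only as a diagnosis. Then

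recorded incidence = p × (1 − a).

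If a is the same in both arms, the recorded difference is (1 − a) × (pB − pA), which is smaller than the true one. If a differs by arm, the error can go either way.

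**Step 4. Pain entered as CIPN.** Let n be the proportion of an arm whose only pain is neuropathic and entered as CIPN, and o the proportion with any other pain.

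- True difference, Arm B minus Arm A: (oB + nB) − (oA + nA)
- Recorded difference: oB − oA
- Missing part: nB − nA

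If the arms have the same amount of such pain, the missing part is zero. If Arm B has more, as the trial hypothesises, the missing part is positive and the provider-assessed comparison understates a pain benefit in Arm A. No biased assessor is needed.

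**Step 5. Why no number is given.** The documents contain neither p nor a. Nor does 16.5 define the counting period. If incidence means ever during treatment, a patient leaves the count only when every occurrence has been absorbed. With k independent occurrences and a per-occurrence share s, a = s^k: this equals s for one occurrence and falls as k rises. A share of events therefore cannot be multiplied into a proportion of patients.

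**Step 6. Do the patient-reported data fill the gap?** Appendix B schedules them at Cycle 1 Day 1, Cycle 4 Day 1, Cycle 4 Day 8 and end of treatment. The PRO-CTCAE looks back 7 days (Appendix E) and the BPI item 24 hours (Appendix F). They are untouched by 13.4, but a symptom between those windows, for instance in Cycle 2, can reach the endpoint only through the clinician's record.

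**The case against.** The strongest reply has four parts.

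- **The rule is conditional.** Nausea, fatigue or anxiety during chemotherapy with no unifying diagnosis is still recorded and graded. This stands. A reader might infer that following 13.4 removes the symptom endpoint from the comparison; the text supports only a partial loss.
- **Only one component is exposed.** The PRO-CTCAE and BPI data on the same symptoms are governed by 10.2, not 13.4, and 16.5 does not say which instrument defines incidence. This also stands. It limits the harm, but 16.2.2 names the provider-assessed grades as a measure, and the silence of 16.5 is a further reason to name the source.
- **The case report forms are not in the documents.** A dedicated symptom form may exist, and naming CTCAE for these symptoms in 16.2.2 could be read as requiring them to be graded. This cannot be excluded. If such a form exists, the protocol should cite it as the endpoint source.
- **The stakes are small.** This is one part of the last-listed secondary endpoint in a pilot. That is fair.

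Three other stronger readings also go too far. A reader might infer that, because the trial is open-label, staff will look harder for diagnoses in one arm; nothing in the documents shows this. A reader might take fatigue with anaemia as a typical loss, but 13.1 admits an abnormal laboratory value as an adverse event only under limited conditions, so the low count is often not recordable in place of the fatigue. A reader might extend the point to neuropathy or oral dysesthesia. Neuropathy is itself a diagnosis that 13.4 preserves. Oral dysesthesia appears in 16.2.2 on the patient-reported side and is not among the comparisons in 16.5.

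**Conclusion.** The point holds in a limited form. As written, 13.4 can under-count provider-assessed CTCAE pain, fatigue, nausea and anxiety when a symptom is subsumed under an established diagnosis. For pain entered as CIPN, the loss would differ by arm if CIPN differs by arm. The primary endpoint, the grade 2 or higher CIPN endpoint and the patient-reported symptom data are not affected, and neither the sample size nor the stated power changes.

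The size is unknown and should not be quoted as a figure. The conclusion rests on two assumptions: that the adverse event record is the source of the CTCAE grades, as the protocol describes, and that 13.4 is followed as written. It is worth correcting because the remedy is cheap and an unrecorded grade cannot be recovered afterwards.

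**What to change.** - **Section 13.4.** Add an exception: pain, fatigue, nausea and anxiety are graded by CTCAE v5.0, with 0 if absent, at each scheduled adverse event assessment (Day 1 of each cycle and end of treatment) in both arms, starting at Cycle 1 Day 1, whether or not a diagnosis is also recorded. Keep the diagnosis rule for all other adverse events and for serious adverse event reporting.
- **Section 16.5.** State that the provider-assessed incidence uses these grades, and name the grade and period that count. The grade 2 cut-off there is attached to CIPN only.
- **Section 13.7.** Reconcile it in the same edit. It starts recording when a patient is first exposed to acupuncture, which Arm B does not receive during the comparison period, so it would conflict with grading both arms from Cycle 1 Day 1.

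The cost is a sentence or two in each section and four lines on the existing form: 4 symptoms × 7 assessments = 28 grades per patient, with no new visit. The small downside is that a symptom may appear both as a graded endpoint and within a recorded diagnosis, so it needs a flag to prevent double counting in the adverse event tables.

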13.5 Grading Adverse Event Severity

All AEs will be graded in severity according to the NCI Common Terminology Criteria for Adverse Events (CTCAE) Version 5.0. If a CTCAE criterion does not exist, the investigator should use the grade or adjectives: Grade 1 (mild), Grade 2 (moderate), Grade 3 (severe), Grade 4 (life-threatening), or Grade 5 (fatal) to describe the maximum intensity of the adverse event.

13.6 Attribution of an Adverse Event

Association or relatedness to the study agent will be assessed by the investigator as follows:

- Definite: The event follows a reasonable temporal sequence from exposure to the investigational procedure, has been previously described in association with the investigational procedure, and cannot reasonably be attributed to other factors such as the subject's clinical state, other therapeutic interventions or concomitant medications; AND the event disappears or improves with withdrawal of the investigational procedure and/or re-appears on re-exposure.
- Probable: The event follows a reasonable temporal sequence from exposure to the investigational procedure and has been previously been described in association with the investigational procedure OR cannot reasonably be attributed to other factors such as the subject's clinical state, other therapeutic interventions or concomitant medications.
- Possible: The event follows a reasonable temporal sequence from exposure to the investigational procedure, but could be attributable to other factors such as the subject's clinical state, other therapeutic interventions or concomitant medications.
- Unlikely: Toxicity is doubtfully related to the investigational procedures(s). The event may be attributable to other factors such as the subject's clinical state, other therapeutic interventions or concomitant medications.
- Unrelated: The event is clearly related to other factors such as the subject's clinical state, other therapeutic interventions or concomitant medications.

For general AE assessment, an AE is considered related if it is assessed as definitely, probably, or possibly related; unrelated if it is assessed as unlikely related or unrelated.

13.7 Adverse Event Recording Period

AEs will be monitored and recorded in study-specific case report forms (CRFs) from the time of first exposure to acupuncture. AEs with an onset date prior to the first exposure to an investigational procedure will not be recorded, except in the case of clinically significant worsening of the AE during the specified AE monitoring time frame.

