| Population | 56 patients with a GI cancer malignancy with planned ≥3 months of a 5-FU- and oxaliplatin-based chemotherapy regimen. Eligibility criteria includes: 1) GI cancer (primary esophagus, gastric, pancreas, biliary, small bowel, appendix, colon, or rectal) scheduled to receive a new start of 5-FU, oxaliplatin, ± irinotecan [FOLFOX, FOLFIRINOX, FOLFOXIRI regimens] with plan for ≥3 months of therapy with the regimen, 2) age ≥18 years, 3) absolute neutrophil count >500 and platelet count >20,000, 4) not currently pregnant, 5) ability to understand and the willingness to sign a written informed consent document, 6) no baseline neuropathy from any cause, 7) no prior neurotoxic chemotherapy of any kind in the prior 3 years, 8) no planned initial dose of oxaliplatin <100% of the standard regimen-specified dose, 9) no receipt of acupuncture treatment in the prior 3 months, 10) no use of concomitant duloxetine for minimization of neuropathy, 11) no psychiatric illness/social situations that would limit compliance with study requirements. |
| Primary Endpoint | Chemotherapy-induced peripheral neuropathy as measured by the EORTC-CIPN 20. |
| Secondary Endpoints | 
 Incidence of grade 2 or higher CIPN as measured by CTCAE version 5. Severity of chemotherapy-induced peripheral neuropathy as measured by a Neuropen and tuning fork. Proportion of patients assigned to the intervention arm who complete 60% of acupuncture treatments. Incidence of pain, fatigue, nausea, oral dysesthesia, and anxiety as measured by the NCI PRO-CTCAE, Brief Pain Inventory (BPI), and CTCAE version 5. |

| | |
|-----------------------------|--|
| Type of control | Usual care + waitlist arm – receives no acupuncture during the 3-month intervention period |
| Investigation Drug | N/A |
| Dose | Acupuncture: 12 treatments with 30-minute needle retention |
| Route of administration | Acupuncture: filiform needle insertion |
| Regimen | 12 sessions of acupuncture. Acupressure training and self-treatment. |
| Trial Blinding | None |
| Treatment Groups | Arm A: Acupuncture + Acupressure Intervention with standard-of-care cryotherapy: acupuncture during chemotherapy infusion (day 1) and 5-FU pump disconnect (day 3) of each biweekly chemotherapy infusion x6 cycles (i.e. 12 acupuncture treatments over 12 weeks) + self-acupressure Arm B: Waitlist Control Arm with standard-of-care cryotherapy: 6 acupuncture sessions after the completion of the trial |

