9.4 Waitlist Control

To increase participant willingness to be randomized and to increase trial retention, participants randomized to the control arm will receive coupons for six acupuncture treatments at SCCA South Lake Union clinic to be used any time after completion of the individual's duration (approximately 12 weeks) on the study (Appendices M and N). At the time of these visits, AEs and limited exam findings may be collection, which will be entered into the database as well. These visits will ideally be during or coordinated with standard-of-care visits. However, if patients have completed treatment, they may attend acupuncture-only visits.

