9.7 Duration of Follow-Up

Patients will not be followed after the intervention and end-of-treatment questionnaires are complete, with the exception of collection of data during waitlist control acupuncture visits if these are pursued.

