9.9 End of Treatment (EOT) Visit Schedule and Procedures

The EOT visits for all subjects who discontinue from the study should ideally occur 14 days after day 1 of the prior cycle of chemotherapy (which would be 11 days from the last acupuncture treatment). The EOT visit is permitted in the range of 7-30 days after the last use of (Arm A) acupuncture treatment or (Arm B) cryotherapy use but must occur prior to beginning another treatment or receiving another dose of chemotherapy. Procedures to be performed during the EOT Visit include:

- Physical Exam
- Administration of the final QOL measures
- Vital Signs
- Performance Status
- AE Assessment
- Concomitant Medication

As per 6.7. patients who are on the waitlist control arm and choose to use their acupuncture coupons will have the optional EOT visit for uniform data collection, but will also have limited data collected at the time of each acupuncture session to note any toxicities or major symptoms at the time of those visit.

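### Section 13.7 starts adverse event recording at first acupuncture, so as written the control arm has no recording start during the comparison, contrary to 10.1, Appendix B, 9.9 and 13.4

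*Combined protocol and SAP*

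**What the plan says.** Section 13.7 is the only place that defines the recording period. Its first sentence sets the start: "AEs will be monitored and recorded in study-specific case report forms (CRFs) from the time of first exposure to acupuncture". Its second sets an exclusion: "AEs with an onset date prior to the first exposure to an investigational procedure will not be recorded", apart from clinically significant worsening later. Neither sentence gives a start for Arm B.

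The synopsis says that Arm B "receives no acupuncture during the 3-month intervention period". Under 9.4 its six sessions are optional and come "to be used any time after completion of the individual's duration (approximately 12 weeks) on the study". For those visits 9.4 adds: "AEs and limited exam findings may be collection, which will be entered into the database as well". Section 9.7 ends follow-up at the end-of-treatment questionnaires, "with the exception of collection of data during waitlist control acupuncture visits if these are pursued".

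Section 16.2.2 lists grade 2 or higher CIPN by CTCAE version 5 as a secondary endpoint, and names CTCAE as the provider-assessed measure for pain, fatigue, nausea and anxiety. Section 16.5 compares these incidences between arms by chi-squared or Fisher's exact test.

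**The concern.** The rule ties recording to an exposure that only one arm has while the arms are being compared. In Arm A, first acupuncture is planned for cycle 1 day 1. In Arm B it falls after about 12 weeks, if at all. A coordinator who applies 13.7 as written would have no reason to enter an Arm B event before then.

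At stake are the CTCAE-based secondary endpoints and the concurrent control for acupuncture safety. Missing or thinner recording in Arm B would make the control arm look healthier than it is, and acupuncture look worse. The trial is unblinded, so the person entering events knows the arm.

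**Working it through.** **1. The plan's own figure.** The documents give no figure for adverse event recording. The only power statement is in 16.3: 50 complete patients, 0.7 SD, one-sided alpha 0.05, 80% power, 10% loss, 56 enrolled. With 25 per arm, power = Φ(0.7 × √(25/2) − 1.645) = Φ(2.475 − 1.645) = Φ(0.830) = 79.7%; the exact t-test gives 78.7%. Enrolment is 50 / 0.90 = 55.6, rounded up to 56. The figure reproduces. It concerns the EORTC CIPN-20 score, which 13.7 does not touch.

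**2. When does each passage start Arm B recording?**

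| Place | What it implies for Arm B in the comparison period |
|---|---|
| 13.7 | No start: the first acupuncture comes after the period, or never |
| 10.1 | CTCAE version 5.0 attribution is an on-study evaluation done by the study calendar, with no arm restriction |
| Appendix B, AE row | Day 1 of cycles 1 to 6 and end of treatment; the Arm A-only footnote is on acupuncture treatment and acupressure training, not on this row |
| 9.9 | End-of-treatment visit for both arms, including AE assessment, timed "7-30 days after the last use of (Arm A) acupuncture treatment or (Arm B) cryotherapy use" |
| 13.4 | Every adverse event goes into the CRFs, with no arm restriction |
| 13.1 | "Medical conditions present at screening (i.e., before the study treatment is administered) are not adverse events"; the anchor is study treatment, which is not defined for Arm B |

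The conflict is direct between 13.7 and 10.1, Appendix B, 9.9 and 13.4. Section 13.1 uses a different anchor and does not settle the Arm B start.

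**3. Does the second sentence of 13.7 rescue Arm B?** It refers to an investigational procedure rather than to acupuncture, so one might count cryotherapy. But section 11.0 glosses the study procedures as acupuncture, and the synopsis calls cryotherapy standard of care in both arms. The first sentence would still start recording at acupuncture.

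**4. Is Arm A aligned with the calendar?** Usually. However, 9.2 does not make up missed sessions. A patient who misses day 1 but attends day 3 of cycle 1 would start recording on day 3, while Appendix B starts on day 1.

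**5. Which endpoints depend on this?** The only CTCAE grading the documents schedule is the AE assessment (10.1, 13.5, Appendix B). The patient-reported measures, the Neuropen and the tuning fork have their own calendar rows for both arms. The link from AE recording to the CTCAE endpoints is therefore an inference: 16.2.2 does not name the data source, and the CRFs are not in the documents.

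**6. Direction, by illustration only.** Every input here is assumed: equal true grade 2 or higher rates of 20% to 40% in both arms, 28 per arm, and a two-sided Fisher test at 0.05 (16.5 states neither alpha nor sidedness).

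- If Arm B had no entries and blanks were counted as no event, 6 of 28 against 0 of 28 would be significant: p = 2 × C(28,6)/C(56,6) = 2 × 376,740 / 32,468,436 = 0.023. With 5 of 28, p = 2 × 98,280 / 3,819,816 = 0.051. The chance of 6 or more in Arm A is 49.9%, 88.7% and 98.9% at true rates of 20%, 30% and 40%.
- If Arm B events were recorded at 100%, 75% or 50% of the Arm A rate, the chance of a false result against acupuncture would be 1.0–1.3%, 3.0–7.7% and 8.2–28.2%. With 25 per arm it would be 1.1–1.5%, 3.2–6.8% and 8.5–23.1%.

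The documents give no event rate and no capture fraction, and neither reading of the text yields 75% or 50%. These figures show direction, not expected size.

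**The case against.** The strongest reply is that this is a drafting slip. Four places point to recording in both arms and one section points the other way. Because Arm A's first acupuncture is planned for the day the calendar starts AE assessment, 13.7 most plausibly describes that day in Arm A terms and overlooks Arm B. Section 10.1 weighs most here, since it ties CTCAE work to the calendar outside section 13. All of this stands as evidence of intent. It does not remove the contradiction, because none of those places defines a recording period and 13.7 does.

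A second reply is that an empty control arm would be noticed by the independent monitoring and annual review in section 14.0. That may be so; partial under-entry would be harder to see.

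A reader might infer more than the documents support:

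- **That control-arm events will go unrecorded.** The calendar schedules them, so this is a risk and not a forecast.
- **That different sites will diverge.** The documents describe one institutional setting.
- **That the illustrated error rates measure the bias.** Their inputs are assumed, and wholly missing control data would more properly prevent the comparison than bias it.

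**Conclusion.** The contradiction is certain: read literally, 13.7 leaves Arm B with no recordable adverse event in the 3-month comparison, against 10.1, Appendix B, 9.9 and 13.4. The consequence is conditional on two things: that staff follow 13.7 over the calendar, and that the AE assessment is the source of the CTCAE endpoints, which is likely but unstated. If both hold, the CTCAE comparisons in 16.5 lose their control data or are biased against acupuncture by an amount that cannot be derived. The reach is limited to secondary endpoint 1, the provider-assessed part of secondary endpoint 4, and the safety comparison. The rule is wrong as written and cheap to correct, but it does not threaten the primary analysis or the sample size.

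**What to change.** In 13.7, replace both exposure-based starts with one start that applies to both arms and runs through the end-of-treatment visit. Cycle 1 day 1 matches Appendix B; another arm-neutral start, such as randomization, would also remove the asymmetry, and the choice is the sponsor's. State that adverse events from Arm B waitlist acupuncture visits (9.4, 9.7, 9.9, Appendix B footnote 9) are kept out of the between-arm comparison. A sentence in 16.2.2 naming the data source for the CTCAE endpoints would be a useful optional addition.

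The cost is a few words in 13.7. It needs no new visits, since Appendix B already schedules the assessments, and no change to the 56 patients.
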